5.0 ANALYSIS POPULATIONS

5.1 Full Analysis Set (FAS) Efficacy Population

The FAS includes all randomized and treated subjects. FAS will be used for all efficacy evaluations.

5.2 Per-Protocol (PP) Efficacy Population

The Per Protocol (PP) population is a subset of the subjects in the FAS population who complete the Month 1 visit and have no protocol deviations (PD) considered to have a substantial impact on the primary efficacy outcome. The primary efficacy endpoint will be evaluated using the PP population if the PP population consists of less than 95% of the FAS population.

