##### 9.1.1.2 *Per-protocol (PP) Efficacy Population*

The Per Protocol (PP) population is a subset of the subjects in the FAS population who complete the Month 1 visit and have no protocol deviations considered to have a substantial impact on the primary efficacy outcome. The primary efficacy endpoint will be evaluated using the PP population if the PP population consists of less than 95% of the FAS population.

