8.0 CLINICAL QUESTIONNAIRES

8.1 Alluzience Preparation Questionnaire

The Alluzience Preparation Questionnaire (Appendix B) consists of 4 questions including the time for study product to equilibrate to room temperature and the time it took to prepare the product to have it ready for injection. The questionnaire will only be given on Visit 2.

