9.0 EFFICACY VARIABLES

9.1 Primary Efficacy Variables

To address the primary endpoint of evaluating the time needed to prepare Alluzience and powder BoNT-A according to protocol, the time (in minutes) needed to prepare Alluzience will be calculated as:

- Alluzience: The sum of the "Time for study product to equilibrate to room temperature" and the answer to the question "How long did it take to prepare the product to have it ready for injection?" on the Alluzience Reconstitution Questionnaire.

- Powder BoNT-A: The sum of the "Time for solvent to equilibrate to room temperature" and the answer to the question "How long did it take to prepare the product to have it ready for injection?" on the BOTOX/Vistabel Reconstitution Questionnaire.

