10.1 Primary Efficacy Analysis

The primary endpoint is the time (in minutes) needed to prepare Alluzience and powder BoNT-A according to protocol. CCI

[figure not shown]

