10.1.1 Sensitivity Analysis

The primary efficacy analysis will be repeated on the Per-Protocol population.

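### The per-protocol set requires a completed Month 1 visit, although its only visible use is for preparation time, which is fully recorded on Day 0

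*SAP*

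**What the plan says.** SAP 5.2 defines the PP set as FAS subjects "who complete the Month 1 visit and have no protocol deviations (PD) considered to have a substantial impact on the primary efficacy outcome". Protocol 9.1.1.2 matches it: "who complete the Month 1 visit and have no protocol deviations considered to have a substantial impact on the primary efficacy outcome". Two conditions must therefore both be met: attendance at Month 1, and no deviation that matters for the primary outcome.

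On the use of the set, SAP 5.2 continues: "The primary efficacy endpoint will be evaluated using the PP population if the PP population consists of less than 95% of the FAS population". SAP 10.1.1 sets no such threshold: "The primary efficacy analysis will be repeated on the Per-Protocol population".

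On the endpoint, SAP 10.1 states: "The primary endpoint is the time (in minutes) needed to prepare Alluzience and powder BoNT-A according to protocol". SAP 9.1 builds the variable in each arm by adding the equilibration time to the hands-on preparation time, both taken from the arm's questionnaire. SAP 8.1 says of the Alluzience form: "The questionnaire will only be given on Visit 2". SAP 8.2 says the same of the powder form. Protocol 7.1.1 has the Treating Investigator complete the questionnaire after treatment at that visit, which Protocol 8.1.2 places on Day 0.

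**The concern.** A per-protocol set should keep the subjects whose data on the endpoint were obtained as the protocol intends. Here the endpoint is finished once the syringe is ready, and attendance about four weeks later says nothing about how the product was prepared. A subject with a properly timed preparation who misses Visit 3 is nevertheless removed.

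Two things are at stake. First, the only visible sensitivity analysis of the primary endpoint loses usable observations to an irrelevant criterion, so a reader cannot tell whether a change between FAS and PP reflects preparation or attendance. Second, under SAP 5.2 the size of the PP set decides whether that analysis is run at all, so follow-up attendance alone can decide it.

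**Working it through.** **Inputs**
- Planned FAS: about 150, of whom 100 are on Alluzience and 50 on powder (SAP 3.4). The number does not come from a calculation, so there is no planned figure to reproduce.
- PP trigger: below 95% of the FAS (SAP 5.2).
- Month 1 non-completion: not given. The only rate in the documents is the 10% screen failure rate (SAP 3.3), which applies before randomization. The rates below are assumptions.

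**Step 1: can Month 1 affect the endpoint?** Both components are entered on a Visit 2 form. The questionnaires in Protocol Appendix 1 run the preparation clock from opening the outer box to a syringe ready for use. No visible procedure at Visit 3 (Protocol 8.1.3) adds to, completes or corrects either component.

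**Step 2: does the clause add anything to the impact test?** The second condition in SAP 5.2 already removes subjects with deviations that matter for the primary outcome. A missed visit is one of the deviation types in SAP 7.5, Table 1. Under the impact test a missed Month 1 visit would exclude nobody, because it cannot alter a Day 0 time. The subjects removed by the Month 1 clause alone are therefore exactly those who pass the relevant test.

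**Step 3: the trigger.** 0.95 × 150 = 142.5.
- 7 exclusions: 143/150 = 95.3%, not triggered.
- 8 exclusions: 142/150 = 94.7%, triggered.

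Eight missed Month 1 visits are enough by themselves.

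**Step 4: how likely is that?** If X is the number missing Month 1, taken as binomial with n = 150 and independent non-completion at rate d:

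| Assumed d | Expected loss, 150 × d | P(X ≥ 8) |
|---|---|---|
| 2% | 3.0 | 1.1% |
| 3% | 4.5 | 8.3% |
| 5% | 7.5 | 47.7% |
| 8% | 12.0 | 91.9% |
| 10% | 15.0 | 98.6% |

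**Step 5: precision.** With equal loss in both arms and a common SD, the standard error of a difference in means grows by the factor √{[1/(100(1−d)) + 1/(50(1−d))] / [1/100 + 1/50]} = √[1/(1−d)].
- d = 5%: 7.5 subjects lost; √(1/0.95) − 1 = 2.6%.
- d = 15%: 0.15 × 150 = 22.5 subjects lost; √(1/0.85) − 1 = 8.5%.

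**Step 6: with the clause removed.** Exclusions due to Month 1 alone fall to 0 at any d, and the trigger responds only to preparation deviations and unrecorded times.

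**The case against.** The strongest reply is that little depends on this. The primary analysis uses the FAS, which has no Month 1 condition (SAP 5.1 and 10.0). A reader might infer that primary data are dropped from the main result. They are not: every observed time stays in, and only the repeat on the PP set loses subjects. This stands.

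A reader might also infer that the PP set ignores whether the product was prepared correctly. It does not. The impact condition is in the same sentence as the Month 1 clause, and Protocol Appendix 1 asks that departures from the reconstitution steps be recorded as deviations. The fault is an irrelevant condition added to a relevant one.

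A third tempting inference is bias, since the study is open-label and Month 1 is the exit visit in one arm but the first of four follow-ups in the other. Attendance could differ by arm, but the documents link it to preparation time in no way. If the two are unrelated, the loss is close to random and costs only precision.

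The loss also depends on an unstated rate: at 2% it is about 3 subjects and the trigger would rarely be reached. The protocol plans descriptive statistics only (9.1.2 and 9.1.4), and a standard error is not among its listed summaries. Triggering the rule adds an analysis and removes none, and if SAP 10.1.1 governs, the threshold has no effect.

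All of this limits the size of the point. None of it supplies a reason for the clause. Parts of SAP 10.1 and 10.2 are redacted, so another use of the PP set cannot be excluded, but that would not make Month 1 relevant to a Day 0 time.

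**Conclusion.** The point holds as a defect in the definition of a sensitivity set. The Month 1 condition has no bearing on the one endpoint for which the PP set is visibly used. It removes only records that pass the plan's own impact test, and it can trip the 95% rule with 8 missed visits out of 150. The main FAS result is untouched. The precision cost is small, about 3% to 8% on the standard error, and rests on three assumptions: 5% to 15% missing Month 1, equal loss in both arms, and a common SD. The documents support no claim about the existence or direction of bias. The correction is worth making because it is nearly free and lets the PP result be read as a statement about preparation.

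**What to change.** In SAP 5.2, delete the Month 1 condition. Define the PP set as FAS subjects with a recorded Visit 2 preparation time (both components that SAP 9.1 adds together) and no protocol deviation considered to have a substantial impact on the primary outcome. State that impact is judged from how the product was prepared, not from the length of the recorded times, and that exclusions are documented before database lock.

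That restriction matters because equilibration time is part of the primary variable, so excluding subjects for long or short equilibration would select on the outcome. The protocol's equilibration passages also disagree: section 6.1.7 and Appendix 1 give 15 to 30 minutes, while step 6 of section 8.1.2 gives 30 minutes. They must be reconciled before any of them is used to define a deviation.

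Log the departure from Protocol 9.1.1.2 in the SAP change table (section 16.0). Reconcile the conditional PP rule in SAP 5.2 with the unconditional one in SAP 10.1.1.

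Cost: a few sentences in the SAP and one row in the change table, with no new data. Editing Protocol 9.1.1.2 itself would need an amendment; recording the change in the SAP before lock avoids that.

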5.3 Safety Population

The safety population includes all subjects who were administered study product (i.e., Alluzience or powder BoNT-A). Safety analysis will be performed based on the Safety population.

6.0 SUBJECT DISPOSITION

Overall subject disposition will include the number of subjects screened, the number of subjects randomized to each treatment arm, the number of subjects in each analysis population (safety, FAS, and PP populations), and the number of subjects who withdrew from the study and the reasons for withdrawal.

Subject disposition by visit will show the number of subjects who completed each visit for the FAS population. Listings of screen failures (including inclusion/exclusion criteria) will be also presented.

7.0 DEMOGRAPHIC AND BASELINE CHARACTERISTICS

The FAS population will be used to summarize the data under this section. The summary will be done with appropriate descriptive statistics. Specifically, number and percentages will be provided for categorical variables, and mean, SD, median, min/max for continuous variables. All tables will be presented by treatment arm and overall.

7.1 Demographic Characteristics

Demographic characteristics at study entry will be summarized by treatment and overall. No formal statistical comparisons between treatment groups will be performed. Tables and listings will be presented.

Demographic variables to be summarized are:

- Age (years)
- Sex
- Child-bearing potential, for females only
- Race
- Ethnicity
- Age category (<30 years, 31-64 years and \leq median age, $>$ median age)
- Weight (kg)
- Body mass index (BMI) (kg/m²)
- Height (cm)
- Subject is toxin naïve or non-toxin naïve

7.2 Cosmetic/Aesthetic Procedures and Implant History

Cosmetic/Aesthetic procedures and implant history will be summarized by treatment in a table and reported by treatment and subject in a data listing. The table will be sorted by overall incidence first and then alphabetically. The listing will show the verbatim term (i.e., term reported by the site), as well as the Medical Dictionary for Regulatory Activities (MedDRA) version 24.1 or later System Organ Class (SOC) and Preferred Term (PT) associated with the verbatim term. The listing will include the procedure/product name, procedure/product location and date of procedure.

7.3 Medical History

Medical history information will be summarized by treatment in a table and reported by treatment and subject in a data listing. The table will be sorted by overall incidence first and then alphabetically. The listing will show the verbatim term (i.e., term reported by the site), as well as the Medical Dictionary for Regulatory Activities (MedDRA) version 24.1 or later System Organ Class (SOC) and Preferred Term (PT) associated with the verbatim term. Start and end dates (or ongoing at the time of consent) will also be included in the listing.

7.4 Concomitant Procedures

Medical and surgical procedures, including, but not limited to, laser/radiation procedures, dermal fillers (area of treatment should be indicated), X-rays, surgeries, other facial procedures, and tooth extractions will be summarized by treatment in a table and reported by treatment and subject in a data listing. The table will be sorted by overall incidence first and then alphabetically. The listing will show the verbatim term (i.e., term reported by the site), as well as the Medical Dictionary for Regulatory Activities (MedDRA) version 24.1 or later System Organ Class (SOC) and Preferred Term (PT) associated with the verbatim term. Start and end dates (or ongoing at the time of consent) will also be included in the listing.

7.5 Protocol Deviations

Protocol Deviations (PDs) are defined as a divergence or departure from the clinical trial design or procedures as described in the approved trial protocol and protocol amendments. A Grade 1 PD is defined as a breach which does or will affect the safety and/or rights of a trial subject or the reliability and robustness of data generated in the clinical trial or the scientific value of the trial. A Grade 2 PD is defined as a breach which might affect the safety and/or rights of a trial subject or the reliability and robustness of data generated in the clinical trial or the scientific value of the trial. A Grade 3 PD is defined as a breach/deviation which does not affect the safety or rights of a trial subject or the reliability or robustness of the trial data or affect the scientific value of the trial.

For this study, the protocol deviations are identified (but not limited to) in Table 1 below. Protocol violators resulting in exclusion from the PP population will be identified by the sponsor and documented prior to the database freeze.

Table 1: Protocol deviations

Deviation Type
SAE Reporting
Study Product Use
Missed Procedure
Eligibility
Photography
Informed Consent
Missed Visit
Prohibited medication or procedure
Out of Window visit
Remote visit all assessments done
Remote visit all assessments not done, specify

The number and percentage of subjects with a PD and the type of PD will be summarized for the FAS population by site, treatment arm and overall. Percentages will be based on the total FAS population. A listing of PDs will be provided.

7.5.1 Out of Window visit duration

When a subject performs a planned study visit outside of the protocol-specified visit windows (Appendix A), the subject has an out of window study visit, which is considered a type of protocol deviation for this study. Knowing a subject's Screening visit (Visit 1) and Baseline visit (Visit 2) and using the protocol-specified visit windowing, one can calculate a subject's target study visit window date range for each planned study visit. Then, by comparing a subject's actual study visit date to the target study visit window date range, one can calculate the days over/under the actual study visit was in relation to the target study visit date, or study visit out of window duration.

The duration, in days, a study visit is out of window will be summarized by treatment group, overall, and by visit. Out of window visit durations will also be presented by site as well. Duration will be split into the following below categories. Duration categories will include both days before and days after the target planned visit date.

- +/- 1-2 days
- +/- 3-7 days
- +/- 8-20 days

- +/- 21 or more days

The number and percentage of subjects within each out of window duration category will be presented descriptively. For the overall analysis, percentages will be calculated using the number of subjects with an out of window visit at the respective visit as the denominator; for the by site analysis, percentages will be calculated using the number of subjects at the respective site as the denominator.

8.0 CLINICAL QUESTIONNAIRES

8.1 Alluzience Preparation Questionnaire

The Alluzience Preparation Questionnaire (Appendix B) consists of 4 questions including the time for study product to equilibrate to room temperature and the time it took to prepare the product to have it ready for injection. The questionnaire will only be given on Visit 2.

8.2 BOTOX/Vistabel Reconstitution Questionnaire

The BOTOX/Vistabel Reconstitution Questionnaire (Appendix C) consists of 5 questions including the time for the solvent to equilibrate to room temperature and the time it took to prepare the product to have it ready for injection. The questionnaire will only be given on Visit 2.

8.3 Investigator Treatment Session Questionnaire (for Alluzience only)

The Investigator Treatment Session Questionnaire (Appendix D) should be completed by the Treating Investigator after the subject has been treated at Visit 2 (baseline). The Investigator Treatment Session Questionnaire consists of 12 questions, where each question has 5 possible values ranging from Strongly disagree to Strongly agree.

CCI

9.0 EFFICACY VARIABLES

9.1 Primary Efficacy Variables

To address the primary endpoint of evaluating the time needed to prepare Alluzience and powder BoNT-A according to protocol, the time (in minutes) needed to prepare Alluzience will be calculated as:

- Alluzience: The sum of the "Time for study product to equilibrate to room temperature" and the answer to the question "How long did it take to prepare the product to have it ready for injection?" on the Alluzience Reconstitution Questionnaire.

- Powder BoNT-A: The sum of the "Time for solvent to equilibrate to room temperature" and the answer to the question "How long did it take to prepare the product to have it ready for injection?" on the BOTOX/Vistabel Reconstitution Questionnaire.

9.2 Secondary Efficacy Variables

Secondary efficacy variables to support secondary endpoints include:

9.2.1 Proportion of study products prepared by the investigators in front of the subjects

For the Alluzience treatment group, calculated as (number of subjects where the product was prepared in front of them / total number of subjects injected with Alluzience).

For the powder BoNT-A treatment group, calculated as (number of subjects where the product was reconstituted in front of them / total number of subjects injected with powder BoNT-A).

9.2.2 Proportion of technical issues/problems

Calculated as (number of subjects in response category X / total number of subjects injected with Alluzience), where response category X refers to the answer to whether the Investigator experienced any technical issues/problems when using a ready to use product as compared to a product to be reconstituted (strongly agree/agree/ neither agree nor disagree/ disagree/ strongly disagree). This will be calculated for the Alluzience treatment group only.

9.2.3 Proportion of powder BoNT-A reconstitution issues

Calculated as (number of subjects with a product problem associated with the reconstitution / total number of subjects injected with powder BoNT-A). This will be calculated for the powder BoNT-A treatment group only.

Calculated as (number of times an investigator experienced any issues to reconstitute the powder BoNT-A in the past / total number of subjects injected with powder BoNT-A). This will be calculated for the powder BoNT-A treatment group only.

9.2.4 Investigator Treatment Session Questionnaire

The proportion of subjects in each answer will be calculated as (number of subjects in response category X / total number of subjects injected with same treatment). The Investigator Treatment Session Questionnaire (Alluzience only) at baseline will be analyzed.

CCI

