### List of Figures

Figure 1	Study Flow Chart .....	16
Figure 2	Injection Sites for Treating Glabellar Lines.....	37

GALDERMA EST. 1981	Title 05PF2005 Clinical Study Protocol - STAR	Doc id MA-48441
STUDY SYNOPSIS		
Clinical Study Title:	A Phase IV, Randomized, Interventional, Study to Assess Subject Treatment Session Perception and Investigator Treatment Experience of Alluzience and Vacuum-Dried Botulinum Neurotoxin Type A for Aesthetic Use	
Short Title:	Study comparing Treatment with Alluzience vs Reconstituted toxin (STAR)	
Clinical Trial Number:	05PF2005	
Countries Involved and Planned Number of Study Sites:	Countries: Germany and the United Kingdom No. of study sites: up to 10 sites	
Clinical Study Design:	
This is a Phase IV, open-label, randomized, interventional, two-armed, multi-centre study to investigate subject treatment perception and Investigator treatment experience when using Alluzience or vacuum-dried botulinum neurotoxin type A (powder BoNT-A) for treatment of glabellar lines (GL).
 
Approximately 150 subjects will be randomized to either Alluzience or powder BoNT-A treatment in a CCI ratio. It is estimated that around 170 subjects will be screened to obtain the number of randomized subjects needed for the study. Randomization will be stratified by study site.
 
The study consists of six visits; screening, treatment and four follow-up visits 1, 3, 5 and 6 months after treatment, subjects randomized to be treated with powder BoNT-A will only be followed for 1 month. The screening visit and the treatment visit might be conducted at the same day. The Investigator and subject will after the treatment fill in questionnaires about how they perceived the treatment session and the Investigator will also answer questionnaires regarding treatment details, reconstitution CCI  CCI of the used study product.  CCI
 
Adverse events (AEs) will be collected from treatment until the end of the subject's participation. Any related, unresolved AE will be followed until resolution for up to 3 months after the study or until considered stable.
	
Total Number of Subjects (Planned):	Approximately 150 subjects will be randomized to either Alluzience or powder BoNT-A treatment in a CCI ratio,	

GALDERMA EST. 1981	Title 05PF2005 Clinical Study Protocol - STAR	Doc id MA-48441

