## SCHEDULE OF ASSESSMENTS

**Table 2 Schedule of Assessments**

1 month = 4 weeks/28 days Visit windows are calculated from Baseline/Visit 2 if not otherwise specified.	Visit 1 Group 1 and 2	Visit 2 Group 1 and 2	Visit 3/ Group 1 EoS Group 2	Visit 4 Group 1	Visit 5 Group 1	Visit 6/ET EoS Group 1
	Screening 	Treatment/ Baseline  (within 3 weeks after screening)	1-Month Follow-up (±7 days)	3-Month Follow-up (±7 days)	5-Month Follow-up (±7 days)	6-Month Follow-up (±7 days)
Informed Consent	X	(X) 				
Demographic Data including, medical history & con-current diseases, previous facial treatments/ procedures	X	(X) 				
Inclusion /Exclusion Criteria	X	X				
Adverse Events 		X	X	X	X	X
Concomitant Medication/ Procedures	X	X	X	X	X	X
Urine Pregnancy Test 	X	X				
Photography		X	X	X		X
Randomization		X				
Treatment		X				
End of study 			X Group 2, powder BoNT-A			X Group 1, Alluzience
Investigator Assessments						
Reconstitution/Preparation Questionnaire		X				
Investigator Treatment Session Questionnaire 		X				
CCI						

1. Screening and treatment/baseline visits can be performed at the same day
2. Only to be conducted if no screening visit has been performed. Changes to medical history should be asked for if the screening and baseline visits are not performed on the same day.
3. AEs are collected from treatment to the end of the subject's participation, for details how to follow-up ongoing AEs at the last visit see section [7.2.1.1.5](#).
4. Only for women of childbearing potential
5. Subjects in the powder BoNT-A treatment group will be followed 1 month and subjects in the Alluzience treatment group will be followed for 6months.
6. Only for Alluzience-treated subjects
7. Only to be completed once for each Treating Investigator, per study product, after all enrolled subjects have completed Visit 2.
8. Performed pre-treatment

CONFIDENTIAL

Page 17 of 71

*Effective*

GALDERMA EST. 1981	Title 05PF2005 Clinical Study Protocol - STAR	Doc id MA-48441
-----------------------	---	---------------------------

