## 5. SELECTION AND DISPOSITION OF CLINICAL STUDY POPULATION

### 5.1 Number of Subjects

As a screen failure rate of approximately 10% is anticipated, approximately 170 subjects will be screened in order to enroll approximately 150 subjects in a **CC1** ratio to 50 s.U of Alluzience (N=100) or 20 U powder BoNT-A (N=50). It is expected that each site will recruit a similar number of subjects (approximately 10 to 20 subjects).

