## Appendix 2 Investigator Treatment Session Questionnaire (for Alluzience only)

NOTE: To be answered for Alluzience only	Strongly agree	Agree	Neither agree nor disagree	Disagree	Strongly disagree
1. I prefer to utilize a ready to use product as compared to a product to be reconstituted					
2. I could dedicate more time to explain the treatment procedure in using a ready to use product as compared to a product to be reconstituted					
3. I could save time on the reconstitution and injection procedure to do something else					
4. I felt more relaxed/less stressed in not having to reconstitute the product to be injected					
5. I feel more secure when I have a pre-diluted solution and don't have to reconstitute the product myself					
6. I have a good feeling about injecting a modern and innovative product as compared to the reconstituted product					
7. I feel I am more precise in my injection with a ready to use product compared to a product to be reconstituted					
8. I like to propose new innovative treatment with liquid ready to use product to my patient					
9. I produced substantially less waste of non-toxin material (syringes, needles, saline etc.) using ready-to-use product as compared to the reconstituted product					

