3.3 Treatments and Assignment to Treatments

As a screen failure rate of approximately 10% is anticipated, approximately 170 subjects will be screened. Approximately 150 subjects will be randomized to either Alluzience or powder BoNT-A treatment in a CCI ratio. Randomization will be stratified by study site.

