3.4 Determination of Sample Size

The sample size of approximately 150 subjects, 100 subjects in the Alluzience treatment group and 50 in the powder BoNT-A treatment group, is not based on a statistical calculation. The selected number of subjects is regarded as sufficient for an evaluation of the studied endpoints by using descriptive statistics.

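### SAP 9.2.4 reports investigators' repeated answers as a proportion of about 100 subjects and shows neither how many investigators answered nor what each one thought

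*SAP*

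**What the plan says.** The second secondary objective (Protocol 2.1.2, SAP 3.1.2) is to describe the investigator's treatment experience with Alluzience. The form "should be completed by the Treating Investigator after the subject has been treated at Visit 2 (baseline" visit), according to SAP 8.3, and only for Alluzience subjects (Protocol 7.1.2). This gives one form per Alluzience subject. The planned arms are "100 subjects in the Alluzience treatment group and 50 in the powder BoNT-A treatment group, is not based on a statistical calculation" (SAP 3.4), so about 100 forms are expected.

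The protocol defines the endpoint as the share of answers in each response option. SAP 9.2.4 turns this into a share of subjects: "number of subjects in response category X / total number of subjects injected with same treatment". SAP 10.0 limits the calculation to questions with an answer, and SAP 10.2 plans n and percentages. SAP 14.0 adds that tables will use the term subject throughout.

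The Protocol Synopsis gives "No. of study sites: up to 10 sites", and Protocol 5.1 states: "It is expected that each site will recruit a similar number of subjects (approximately 10 to 20 subjects"). The number of Treating Investigators is not stated. The protocol's definition of Investigator includes sub-investigators, so a site may have more than one.

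**The concern.** The respondent is the investigator, but the counted unit is the subject. Many items do not refer to the session just finished. Item 1 reads "I prefer to utilize a ready to use product as compared to a product to be reconstituted". By my reading, items 1, 5 to 8 and 10 to 12 (8 of 12) are standing opinions on ready-to-use products, and items 2, 3, 4 and 9 can be read as about the session. An investigator who treats ten Alluzience subjects states the same general opinion ten times, and the table counts ten subjects.

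Two things are at stake. First, a result such as 85 of 100 invites the reader to think of 100 separate judgements. Protocol 9.1.2.3 also collapses the five options to three, giving one headline agreement figure per item, and Protocol 11.8 intends publication in a registry and a journal. Without the number of investigators, a reader cannot correct the impression. Second, an investigator's weight in the result depends on how many Alluzience subjects he or she treated, which has nothing to do with the objective.

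The sponsor already treats the investigator as a unit for another form. Footnote 7 to the schedule of assessments says: "Only to be completed once for each Treating Investigator, per study product, after all enrolled subjects have completed Visit 2". The table row that it belongs to is redacted.

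**Working it through.** The plan gives no precision figure to reproduce, because the sample size is not based on a calculation. The check therefore asks how much independent information about 100 forms could carry.

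**Inputs from the documents:** about 100 Alluzience subjects of 150 (SAP 3.4); up to 10 sites (Protocol Synopsis); 10 to 20 subjects per site (Protocol 5.1).

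**Assumptions:** the number of investigators k (8, 10 or 20) and the within-investigator correlation ICC (0.1 to 1.0). The documents give neither. ICC 1.0, where an investigator never changes an answer, is an upper bound because four items can vary by session.

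**Formulas:** forms per investigator m = 100/k; design effect DE = 1 + (m − 1) × ICC; effective n = 100/DE.

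| k | m | ICC | DE | Effective n |
|---|---|---|---|---|
| 8 | 12.5 | 0.1 | 2.15 | 46.5 |
| 8 | 12.5 | 1.0 | 12.5 | 8.0 |
| 10 | 10 | 0.1 | 1.9 | 52.6 |
| 10 | 10 | 0.3 | 3.7 | 27.0 |
| 10 | 10 | 0.5 | 5.5 | 18.2 |
| 10 | 10 | 1.0 | 10.0 | 10.0 |
| 20 | 5 | 0.1 | 1.4 | 71.4 |
| 20 | 5 | 0.5 | 3.0 | 33.3 |
| 20 | 5 | 1.0 | 5.0 | 20.0 |

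**If an interval were added later.** At 80% agreement the 95% half-width is 1.96 × √(0.16/n). Treating the forms as independent gives 1.96 × √(0.16/100) = 7.8 points. With 10 investigators it is 10.8 points at ICC 0.1, 18.4 at 0.5 and 24.8 at 1.0. If every answer agreed, the exact lower 95% limit would be 0.025^(1/100) = 96.4% for 100 independent forms, and 0.025^(1/10) = 69.2% for 10 investigators. The plan states none of these figures; they show how far the implied denominator could mislead.

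**Weighting.** Take one investigator per site, five sites of 20 subjects and five of 10 (150 in total). Two thirds of each site's subjects are on Alluzience (100/150), so the sites supply 13.3 or 6.7 forms each.
- Two dissenters at small sites: 2 × 6.7 = 13.3, about 13% of answers.
- Two dissenters at large sites: 2 × 13.3 = 26.7, about 27% of answers.
- Two of ten with equal weights: 20%.

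The largest site weighs 20/150 = 13.3% and the smallest 10/150 = 6.7%. At ICC 1.0, unequal site sizes lower effective n from 10.0 to 1/Σw² = 9.0.

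**The case against.** The strongest reply is that the plan is descriptive. Protocol 9.1.4 rules out inferential statistics, SAP 10.2 gives n and percentages, and no interval, standard error or test for this form is visible. This stands. A reader might infer that the plan overstates its precision, but the visible text states no precision for this form. SAP 11.1 mentions tests among the secondary analyses, and the SAP change history lists Protocol 9.1.4, but the detail is redacted and cannot be judged. The form is Alluzience-only, so a between-arm test could not apply to it.

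A reader might also infer that large sites dominate. Protocol 5.1 expects similar recruitment, about 2:1 at most, so the weighting is moderate. The 13% and 27% figures need both dissenters to sit at the same extreme of site size.

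Nor do the documents show that only a handful of people answer, or that their answers are identical. The number of sites is not the number of Treating Investigators, and four items may vary by session.

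Finally, the session-level proportion follows the protocol's endpoint, and footnote 7 concerns a redacted form. That footnote does not show that this questionnaire should be completed only once per investigator. This argues against replacing the endpoint. It does not argue against showing who the respondents are: a descriptive percentage still needs a denominator that matches what it describes.

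**Conclusion.** The point holds as one of unit and labelling. SAP 9.2.4 presents repeated answers from an unstated number of investigators as a proportion of about 100 subjects, for an objective about investigator experience, and the visible text has no investigator-level summary. The amount of independent information depends on assumptions. With 10 investigators it is about 53, 18 or 10 answers at ICC 0.1, 0.5 or 1.0; with 20 investigators it is about 71 to 20. Recruitment weighting could move a true two-in-ten dissent to between 13% and 27% of answers at the extremes. The documents do not support the stronger claims of formally overstated precision or of domination by large sites. The change is worth making because it alters what objective 2 can conclude, although the endpoint is secondary, descriptive and confined to one arm.

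**What to change.** - In SAP 9.2.4, keep the protocol-defined session-level proportions, but label them as answers, not subjects. State the number of responding investigators and the answers per investigator (for example median and range).
- In SAP 9.2.4 and 10.2, add an equally weighted per-investigator table for each item, with investigators as the denominator. It could use each investigator's median answer, or each investigator's proportion agreeing averaged over investigators. The averaged proportion needs no tie rule and keeps session-to-session variation.
- Present this table beside the session-level table when concluding on objective 2, not in place of it.
- If any interval is given for this form, cluster it by investigator.
- Apply the same summary to the question in SAP 9.2.3 about past reconstitution problems, where an investigator's history is divided by the number of subjects injected with powder BoNT-A.

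The cost is an extra summary table from data already collected, since SAP 12.1 lists the investigator ID for each treatment. The drawback for the sponsor is a less impressive denominator.
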